**Child Health Questionnaire Child Form 87 Questions**

- In general, how would you say your health is?
- Has it been difficult for you to do the following activities due to health problems - doing things that take a lot of energy, such as playing soccer or running; doing things that take some energy such as riding a bike or skating; walk several blocks or climb several flights of stairs; ability (physically) to get around the neighborhood, playground, or school; walk one block or climbing one flight of stairs; do your tasks around the house; bend, lift or stoop; eat, dress, bathe or go to the toilet by yourself; get in/out of bed?

- Has it been difficult to do certain kinds of schoolwork or activities with friends because of problems like feeling sad or worried; spend the usual amount of time on schoolwork or activities with friends; get schoolwork done at all or do any activities with friends?
- Has it been difficult to do certain kinds of schoolwork or activities with friends because of problems with your behavior; spend the usual amount of time on schoolwork or activities with friends; get schoolwork done at all or do any activities with friends?
- Has it been difficult to do certain kinds of schoolwork or activities with friends because of problems with your physical health; spend the usual amount of time on schoolwork or activities with friends; get schoolwork done at all or do any activities with friends?
- How much bodily pain or discomfort have you had?
- How often have you had bodily pain or discomfort?
- How often did each of the following statements describe you; acted too young for your age; argued; had a hard time paying attention; did not do what your teacher or parent asked you to do; wanted to be alone; lied/cheated; had a hard time getting others to like you; felt clumsy; ran away from home; had speech problems; stole things at home or outside the home; acted mean or moody if you did not get what you wanted; got really mad when you did not get what you wanted; found it hard to be with others; had a hard time getting along with others.
- Compared to other children your age, in general how would you rate your behavior?
- How much of the time do you: feel sad; feel like crying; feel afraid or scared; worry about things; feel lonely; feel unhappy; feel nervous; feel bothered or upset; feel happy; feel cheerful; enjoy the things you do; have fun; feel jittery or restless; have trouble sleeping; have headaches; like yourself?
- How good or bad have you felt about: yourself; your school work; your ability to play sports; your friendships; the things you can do; the way you get along with others; your body and your looks; the way you seem to feel most of the time; the way you get along with your family; the way life seems to be for you; your ability to be a friend to others; the way others seem to feel about you; your ability to talk with others; your health in general?
- My health is excellent; I was so sick once I thought I might die; I do not seem to get very sick; I seem to be less healthy than other kids I know; I have never been very, very sick; I always seem to get sick; I think I will be less healthy when I get older; I think I will be very healthy when I get older; I never worry about my health; I think I am healthy now; I think I worry more about my health than other kids my age.
- Compared to one year ago, how would you rate your health now?
- How often has your health or behavior - limited the types of activities you could do as a family; interrupted various everyday family activities; limited your ability as a family to "pick up and go"; caused tension or conflict; been a source of disagreements or arguments in your family; caused your family to cancel or change plans at the last minute?
- In general, how would you rate your family's ability to get along with one another?

03 DEC 2018

Date (DD-MMM-YYYY)

Approvals

[figure not shown]

[name].
Director, Clinical Research
ApoPharma Inc.

05 Dec 2018

[figure not shown]
[figure not shown]
Date (DD-MMM-YYYY)

[figure not shown]

[figure not shown]

[figure not shown]

[figure not shown]7 - 14 mg/g dw or >14 mg/g dw after they were treated with 35-50 mg/kg or ≥ 50 mg/kg of deferoxamine respectively, for 52 weeks. Assuming the same mean reduction in LIC for Ferriprox but a higher SD of ± 4.0 mg/g

dw for both treatments due to possibly higher variability associated with MRI measurement, the sample size of 300, with >80% being patients with sickle cell disease, will provide over 95% power for demonstrating non-inferiority of Ferriprox to deferoxamine in patients with sickle cell disease.

The sample size estimate is based on a non-inferiority margin of 2 mg/g dw for the reduction of LIC and α of 0.05, two-sided (or α of 0.025, one-sided). It has been reported that in a typical patient with thalassemia major, the LIC could increase by 5 mg/g dw after 1 year without chelation therapy. As the cause of iron overload is the same in thalassemia and sickle cell disease, the same increase in LIC may be expected if patients with sickle cell disease are transfused at the same rate and not treated with a chelator. Hence, the difference in reduction of LIC between deferoxamine therapy and a placebo (effect size) can be estimated to be 9 (i.e., 4 – (-5)) mg/g dw. This means that the non-inferiority margin of 2 mg/g dw would be about 20% of the effect size. With the enrolment of 300 patients, there is a greater than 99% chance (power) of occurrence of at least 1 adverse event with an anticipated incidence rate of 2%, or greater than 95% chance for an anticipated incidence rate as low as 1%.

However, patient's recruitment in this study has proceeded at a very slow pace and despite all our efforts over the past 4 years, the goal of enrolling a total of 300 patients has not been reached. A total of 213 patients (142 patients for Ferriprox and 71 patients for deferoxamine) are projected to have either completed the study or been withdrawn from the study by November 30, 2018. An interim analysis is planned to be performed on the data of these 213 patients. Based on the same values of non-inferiority margin and SD of the LIC measurement, but an α level of 0.0399, two-sided (Pocock's α spending method, see section 3.7 for details), this sample size (213 patients) will provide 89% power to demonstrate non-inferiority of Ferriprox to deferoxamine in this interim analysis, assuming no real difference in efficacy between the two treatments. For the subgroup analysis of only patients with sickle cell disease, the power will be 82% as there are 178 SCD patients (119 patients for Ferriprox and 59 patients for deferoxamine), which is approximately 84% of 213 patients. With the safety data of 213 patients, there is 98% chance (power) of occurrence of at least 1 SAE with an anticipated incidence rate of 2%, or 88% chance for an anticipated incidence rate of as low as 1%.

During this interim analysis, while patient enrollment has been put on hold, there will still be 17 patients who are on-going with their assigned drug treatment. All are projected to have completed the study by October, 2019. If the results of the interim analysis lead to the conclusion of non-inferiority of Ferriprox to deferoxamine, considerations will be given on early termination of the study, to avoid unnecessary exposure of patients to a clinical trial that has reached its objectives. The data from those patients up to the time of

study closure will be added to the interim dataset for the final statistical analysis of the study based on the same statistical analyses in this SAP.

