### Summary Statements

Group sample sizes of 79 and 158 achieve 95% power to detect non-inferiority using a one-sided, two-sample t-test. The margin of equivalence is -2.000. The true difference between the means is assumed to be 0.000. The significance level (alpha) of the test is 0.02500. The data are drawn from populations with standard deviations of 4.000 and 4.000.

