7.1 Primary Efficacy Endpoint

Primary efficacy endpoint is the change from baseline to Week 52 in LIC. Primary efficacy endpoint will be compared between the two treatment groups using an analysis of covariance (ANCOVA) model including treatment variable as the main factor, and overall average transfusional iron input during the study, baseline LIC, and stratification factors (disease category and transfusional iron input in the 3 months prior to baseline) as covariates. The 96.01% $(1 - \alpha)$, where $\alpha = 0.0399$ based on the Pocock’s α spending function for interim analysis) confidence interval (CI) of the difference (Ferriprox minus deferoxamine) in change of LIC from baseline to Week 52 (i.e., Week 52 minus baseline) between the two treatment groups

will be computed. For the demonstration of non-inferiority, the upper limit of the 96.01% CI should be no more than 2 mg/g dw.

The following SAS codes of MIXED procedure will be used to produce the differences in Least Squares (LS) Mean of change in LIC at Month 6 and Month 12 between Ferriprox and deferoxamine groups and the corresponding 96.01% confidence intervals. In the mixed model, AR (1) (autoregressive of order 1) will be used for the covariance structure, and Kenward and Roger's method will be used to estimate the denominator degrees of freedom (SAS model statement option, DDFM = KR).

```

proc mixed data=LIC;
  class patient treat disease prior_iron month
  model LIC_change = treat overall_iron base_LIC disease prior_iron
    month treat*month / noint solution ddfm=kr;
  repeated month / subject=patient(treat) type=ar(1);
  lsmeans treat*month;
  estimate 'Ferriprox - Deferoxamine at Month 6' treat -1 1
    treat*month -1 0 1 0 / cl alpha=0.0399;
  estimate 'Ferriprox - Deferoxamine at Month 12' treat -1 1
    treat*month 0 -1 0 1 / cl alpha=0.0399;
run;

```

Definition of the variables in the statistical model:

LIC_change : Change in LIC from baseline to Week 5
 treat : Ferriprox or Deferoxamine
 month : Duration of treatment in month
 overall_iron : Overall total transfusional iron input (mg/kg/day) during the study
 base_LIC : LIC at baseline
 disease : Sickle cell disease or other anemias
 prior_iron : transfusional iron input in 3 months prior to baseline (≤ 0.3 mg/kg/day or > 0.3 mg/kg/day)

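### The interim power figures in the SAP (89% overall, 82% in sickle cell disease) do not follow from its stated inputs, which give about 91% and 86%

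*SAP*

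**What the plan says.** The last part of the SAP's sample-size section (3.2, directly before 3.3 Treatment) reports power for an interim analysis on 213 patients, 142 on Ferriprox and 71 on deferoxamine. It gives the basis as "Based on the same values of non-inferiority margin and SD of the LIC measurement, but an α level of 0.0399, two-sided", and assumes no real difference between treatments. On that basis it states that "this sample size (213 patients) will provide 89% power to demonstrate non-inferiority of Ferriprox to deferoxamine in this interim analysis". For the SCD subgroup it says "the power will be 82% as there are 178 SCD patients (119 patients for Ferriprox and 59 patients for deferoxamine").

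The carried-over values appear just before this in the same section: "The sample size estimate is based on a non-inferiority margin of 2 mg/g dw for the reduction of LIC", and "a higher SD of ± 4.0 mg/g" dw for both treatments.

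The alpha of 0.0399 is derived in SAP 3.7. It also sets the decision rule in SAP 7.1, under which "the upper limit of the 96.01% CI should be no more than 2 mg/g dw".

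The interim paragraph names no test. The only test named for any power calculation is in protocol Appendix 18.4: "Group sample sizes of 79 and 158 achieve 95% power to detect non-inferiority using a one-sided, two-sample t-test".

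**The concern.** Every numerical input needed to recompute the two figures is written beside them, yet recomputing does not return them. Both stated values are low, and a single changed input can bring both back. That looks like a calculation run with something other than what is written, not like two separate typing errors.

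The alpha in the power sentence is the one behind the 96.01% confidence interval that decides non-inferiority. That result bears on possible early termination (SAP 3.2) and on the DSMB's advice about restarting enrolment (SAP 3.7). As the text stands, a reader cannot tell whether the power run used a different alpha, a different SD, fewer evaluable patients or a different test. The accuracy of the stated power is at stake. The validity of the decision rule is not.

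**Working it through.** **Inputs**

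| Input | Value | Source |
|---|---|---|
| Margin | 2 mg/g dw | SAP 3.2 |
| SD, both arms | 4.0 mg/g dw | SAP 3.2 |
| True difference | 0 | SAP 3.2 |
| Alpha | 0.0399 two-sided, so 0.01995 one-sided | SAP 3.2, 3.7 |
| All patients | 142 / 71 | SAP 3.2 |
| SCD patients | 119 / 59 | SAP 3.2 |
| Loss allowance | none stated | SAP 3.2 |

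The alpha reproduces: 0.05 × ln[1 + (e − 1) × 0.71] = 0.03987, which is the SAP's 0.0399.

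**Formula**

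SE = SD × √(1/n1 + 1/n2). The noncentrality parameter is margin / SE. Power is the probability that a noncentral t variable with that parameter exceeds the one-sided critical value of t. Degrees of freedom (df) are n1 + n2 − 2 for the pooled test, or the Satterthwaite value for the unequal-variance test.

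**Benchmark: the protocol's own output (79/158, one-sided 0.025)**

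SE = 4 × √(1/79 + 1/158) = 0.551, and noncentrality = 2 / 0.551 = 3.63.

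- Pooled, df 235: 0.9509.
- Unequal variance, df 156.1: 0.9501.
- Printed in Appendix 18.4: 0.95017.

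The unequal-variance version agrees to four decimals and the pooled version is within 0.1 point.

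**All patients (142/71, one-sided 0.01995)**

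SE = 4 × √(1/142 + 1/71) = 0.581, and noncentrality = 2 / 0.581 = 3.44.

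- Pooled, df 211: 91.4%.
- Unequal variance, df 140.1: 91.3%.
- Normal approximation: 91.7%.
- Simulation of the confidence-interval rule, 200,000 runs: 91.5%.
- SAP: 89%.

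**SCD patients (119/59, one-sided 0.01995)**

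SE = 4 × √(1/119 + 1/59) = 0.637, and noncentrality = 2 / 0.637 = 3.14.

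- Pooled, df 176: 85.7%.
- Unequal variance, df 115.8: 85.5%.
- Normal approximation: 86.1%.
- Simulation: 85.7%.
- SAP: 82%.

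By the pooled test the gaps are 91.4 − 89 = 2.4 points and 85.7 − 82 = 3.7 points. Across the three formulas they run from 2.3 to 2.7 and from 3.5 to 4.1. The choice of formula moves the result by about half a point, so neither that choice nor rounding explains the gaps.

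**Other readings of the design, which also fail**

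| Reading | All | SCD |
|---|---|---|
| 0.0399 taken as one-sided | 95.3% | 91.5% |
| One-sided 0.025 | 92.8% | 87.8% |
| One-sided 0.0399/4 | 86.2% | 78.5% |
| Equivalence, two one-sided tests at 0.01995 | 83.4% | 72.2% |
| 1:1 allocation, 71/71 and 59/59 | 81.6% | 73.8% |

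**Single unstated changes that do round to 89% and 82%**

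| Change | Pooled | Unequal variance |
|---|---|---|
| Loss of patients | 8.2–9.4% | 7.6–8.9% |
| SD (mg/g dw) | 4.18–4.205 | 4.165–4.195 |
| Two-sided alpha | 0.0265–0.0289 | 0.0272–0.0297 |

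For example, with pooled degrees of freedom a 9% loss gives 88.7% and 82.1%, and an SD of 4.2 gives 88.6% and 82.1%. With unequal-variance degrees of freedom a two-sided alpha of 0.0294 gives 89.1% and 82.4%. A rank test with relative efficiency 9/π² = 0.912 (logistic data) gives 88.7% and 82.2% with pooled degrees of freedom. Each of these is an assumption. The documents do not show which, if any, was used.

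**The case against.** The best defence is that the method is undisclosed, and the figures are not necessarily wrong. The interim paragraph names no test, and the t-test appears only in the protocol's earlier output. The rank-test route above returns the stated pair with every numerical input unchanged. This stands as a further possible cause. It sits poorly with SAP 7.1, though, where non-inferiority is decided by a model-based confidence interval, and the SAP mentions no rank test.

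A second defence is that 89% and 82% may already allow for loss. The 213 include withdrawn patients, and the intent-to-treat definition in SAP 4.1 requires a post-baseline assessment, so the evaluable number may be below 213. That is reasonable, and it is why replacing the figures with 91% and 86% is right only if no loss was intended. But the text attributes the power to 213 patients and to 178 SCD patients and states no allowance. SAP section 5 imputes missing values for patients who leave early.

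Third, the version that best matches the protocol output gives 85.5% for SCD (85.47% before rounding), so 86% is approximate. That is correct, and 85–86% is the fair range. It does not bring 82% within reach.

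Finally, nothing in the documents suggests that the decision itself uses an alpha other than 0.0399. The value is derived in SAP 3.7 and carried into the interval and the code in SAP 7.1 and 7.2. That is accepted. The open question is only what the power run used.

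**Conclusion.** The concern holds. From the SAP's own inputs, interim power is about 91% for all patients (91.3–91.4% by t-test) and about 86% for SCD (85.5–85.7%), against the stated 89% and 82%. This rests on a two-sample t-test, as in the protocol's output, and on all 213 and 178 patients counting towards the analysis, as the SAP sentence says. Both stated figures understate power, so the error is conservative. The sample size, margin, alpha, confidence interval and decision rule do not depend on them. It is a minor correction.

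**What to change.** In SAP 3.2, either restate the interim power as about 91% (all patients) and about 86% (SCD), or add one sentence naming the loss allowance, SD, alpha or test that produced 89% and 82%. If some withdrawn patients were expected not to be evaluable, the second option is the better one. In either case, confirm that the power run used the same 0.0399 that sets the 96.01% interval in SAP 7.1. The cost is two numbers or one sentence, and nothing else in the design or analysis changes.

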### 11.2.4 Determination of Sample Size

Three hundred (300) male and female patients will be enrolled into the study. In a randomized study of two iron chelators for the treatment of iron overload in patients with sickle cell disease (Vichinsky et al., 2006), mean  $\pm$ SD reductions of  $4.0 \pm 1.5$  mg/g dw and  $4.5 \pm 2.0$  mg/g dw were observed (Figure 1 of the article, numerical values obtained from the authors) in patients from the baseline LIC categories of  $>7$ - $14$  mg/g dw or  $>14$  mg/g dw after they were treated with 35-50 mg/kg or  $\geq 50$  mg/kg of deferoxamine respectively, for 52 weeks. Assuming the same mean reduction in LIC for deferiprone but a higher SD of  $\pm 4.0$  mg/g dw for both treatments due to possibly higher variability associated with MRI measurement, the sample size of 300, with  $>80\%$  being patients with sickle cell disease, will provide over 95% power for demonstrating non-inferiority of deferiprone to deferoxamine in patients with sickle cell disease.

The sample size estimate is based on a non-inferiority margin of 2 mg/g dw for the reduction of LIC and an alpha of 0.05, two-sided (or an alpha of 0.025, one-sided, Appendix 18.5). It has been reported that in a typical patient with thalassemia major, the LIC could increase by 5 mg/g dw after 1 year without chelation therapy. As the cause of iron overload is the same in thalassemia and sickle cell disease, the same increase in LIC may be expected in patients with sickle cell disease who are transfused at the same rate and not treated with a chelator. Hence, the difference in reduction of LIC between deferoxamine therapy and a placebo (effect size) can be estimated to be 9 (i.e., 4 – (-5)) mg/g dw. This means that the non-inferiority margin of 2 mg/g dw would be about 20% of the effect size.

With the enrolment of 300 patients, there is also greater than 99% chance (power) of occurrence of at least 1 adverse event with an anticipated incidence rate of 2%, or greater than 95% chance for an anticipated incidence rate as low as 1%.

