3.7 Interim Analysis

An interim analysis will be performed with the data of patients who will have either completed or been withdrawn from the study by November 30, 2018. The Pocock's α spending function (Lan and DeMets, Discrete sequential boundaries for clinical trials. Biometrika, 1983; 70:659-663) will be used for assigning α for this interim analysis. The Pocock's α spending function is:

$$\alpha(t) = \alpha \times \ln [1 + (e - 1) \times t]$$

where $\alpha = 0.05$ and $t = \text{information fraction}$

$$\begin{aligned} &= \text{number of patients at the interim analysis / total number of patients} \\ &= 213 \text{ patients / 300 patients} \\ &= 0.71 \end{aligned}$$

Substituting the values of $\alpha = 0.05$, $t = 0.71$, and $e = 2.718$ into the Pocock's α spending function gives

$$\alpha(t) = 0.05 \times \ln [1 + (2.718 - 1) \times 0.71]$$

$$= 0.05 \times \ln [2.21978]$$

$$= 0.0399$$

Therefore, $\alpha = 0.0399$ will be used for the interim analysis.

A study report will be prepared with the results of the interim analysis and the decision to re-start patient enrollment will be based on the advice of the Data and Safety Monitoring Board (DSMB) after their review of the interim analysis results.

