7.4 Subgroup Analysis

The comparison of the two treatment groups for the primary and secondary efficacy endpoints will be performed by disease type. The same ANCOVA models without disease factor as used in the main analyses will be used.

- Patients with sickle cell disease (SCD) only
- Non- SCD patients.

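### The trial is sized for non-inferiority in sickle cell patients, but the only success rule covers all patients and no testing order links the two

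*SAP*

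**What the plan says.** **Sizing.** Protocol 11.2.4 says the 300 patients "will provide over 95% power for demonstrating non-inferiority of deferiprone to deferoxamine in patients with sickle cell disease". The SAP's sample-size section, just before 3.3, repeats this. Protocol section 1 describes a confirmatory trial whose main focus is transfused SCD patients.

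**Interim power.** The same SAP section gives 89% power for 213 patients (142/71) at a two-sided level of 0.0399. It then adds: "For the subgroup analysis of only patients with sickle cell disease, the power will be 82% as there are 178 SCD patients". The SCD arms are 119 and 59. The level is not restated for SCD.

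**Success rule.** SAP 7.1 states it once, for the primary endpoint: "For the demonstration of non-inferiority, the upper limit of the 96.01% CI should be no more than 2 mg/g dw". SAP section 4 makes the ITT population, with both disease categories, the primary analysis set.

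**Status of SCD.** SAP 7.4 places SCD under subgroup analysis, next to non-SCD: "The same ANCOVA models without disease factor as used in the main analyses will be used". SAP 14.2 plans similar tables for each disease group, and the shell of Table 14.2.1.3 has a 96.01% CI column.

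**Stopping.** The SAP's sample-size section says early termination will be considered if the interim leads to a conclusion of non-inferiority. It does not say in which population.

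Neither document gives a testing order, a split of alpha, or a statement that the SCD result is only supportive.

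**The concern.** The sizing argument and the decision rule point at different populations. A power figure has meaning only for a test that can pass or fail, and the plan quotes one for SCD without giving SCD a rule. Two consequences follow.

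- If only the all-patient result counts, the trial has no formal route to the SCD conclusion that justified its size.
- If, after the results are seen, either population is allowed to carry the claim, two overlapping tests share one error allowance.

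The stopping sentence brings the ambiguity into a trial-level decision. With an all-patient failure and an SCD pass, or the reverse, the text does not say whether non-inferiority has been concluded.

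**Working it through.** **Inputs.** Margin 2 mg/g dw; SD 4.0 in each arm; true difference 0 for power; two-sided level 0.0399, so 0.01995 one-sided and z = 2.055; 142/71 for all patients and 119/59 for SCD. All are in SAP 3.7, 7.1 and the SAP sample-size section. Use of 0.0399 for SCD is inferred from 7.4 and the table shells.

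**1. The plan's own figures**

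- Interim level: 0.05 × ln(1 + 1.718 × 0.71) = 0.0399. Reproduces.
- Design power (Protocol Appendix 18.4, 79 and 158 patients, one-sided 0.025): 95.1% by the t-test, against 95.0% stated. Reproduces. The total of 237 is 79% of 300, so this is the SCD calculation.
- Interim power is Φ(2/SE − 2.055), with SE = 4 × √(1/n₁ + 1/n₂):

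| Set | SE | 2/SE | Power, normal | Power, t | SAP |
|---|---|---|---|---|---|
| All, 142/71 | 0.581 | 3.440 | 91.7% | 91.4% | 89% |
| SCD, 119/59 | 0.637 | 3.140 | 86.1% | 85.7% | 82% |

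The interim figures do not reproduce. A loss of 8% of patients would give 89.0% and 82.6%, and a two-sided level near 0.028 to 0.029 would also come close. The SAP states neither.

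**2. Error if either population may carry the claim**

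Because SCD patients are part of the all-patient set, the two test statistics have correlation SE(all)/SE(SCD) = 0.581/0.637 = 0.913. With a true difference of exactly 2 mg/g in both sets:

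- P(SCD test passes) = 0.01995, and the same for the all-patient test.
- P(at least one passes) = 1 − Φ₂(2.055, 2.055; 0.913) = 0.0278.
- Excess over the interim allowance: 0.0278 − 0.01995 = 0.0079. Excess over 0.025 for the whole trial: 0.0028.

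**3. Fixed sequence, all patients then SCD, each at 0.0399 two-sided**

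- If the all-patient null is true, no claim is possible unless that test passes, so the error is at most 0.01995.
- If only the SCD null is true, a false claim needs the SCD test to pass, so the error is again at most 0.01995.
- Power to pass both with no true difference: P(all) + P(SCD) − P(at least one) = 0.917 + 0.861 − 0.928 = 0.850.

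**4. Alternatives that split alpha**

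| Rule | Two-sided level each | Power, all | Power, SCD |
|---|---|---|---|
| Bonferroni | 0.01995 | 87% | 79% |
| Adjusted for correlation | 0.0283 | 89% | 83% |
| Fixed sequence | 0.0399 | 92% | 85% (both must pass) |

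**5. Non-SCD patients**

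The remainder is 23/12. SE = 4 × √(1/23 + 1/12) = 1.424, so power is Φ(2/1.424 − 2.055) = 26%. A non-inferiority test there would say little.

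**The case against.** The strongest reply is that the plan has one primary test and says so. The primary objective covers SCD and other anemias together, ITT is the declared primary population, and the 2 mg/g rule is attached to that comparison alone. SCD is called a subgroup even in the sentence that gives its power, and quoting power for a subgroup does not make it a second confirmatory hypothesis. This stands, and it limits the point in three ways.

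- A reader might infer that the SCD comparison has no error control. It does: taken alone at the 96.01% CI it holds one-sided 0.01995. Even that level is inferred, because the SCD power sentence states none.
- A reader might infer that the plan already spends 0.0278. It does not. That figure needs a rule that either result suffices, and neither document contains one.
- A reader might infer that an all-patient pass driven by the 35 non-SCD patients would be a false result. With SCD exactly at +2 and non-SCD at 0, for example, the overall difference is 2 × 178/213 = 1.67, inside the margin, so the all-patient pass is correct for the hypothesis stated. The documents give no basis for assuming opposite effects in the two groups, and a testing sequence would not change that pass. Separate tables by disease are planned and would show such a pattern.

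It can also be said that testing SCD first, or declaring SCD supportive only, would be equally legitimate. Both are. The reply still does not explain why a result labelled as a subgroup is the stated reason for the sample size, or which population triggers stopping.

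**Conclusion.** The point holds as a gap between the aim and the decision rule. The trial was sized for an SCD conclusion that its analysis plan cannot formally draw. The error consequence is conditional and modest: about 0.028 one-sided against 0.01995, only if either population may carry the claim, with both true differences at the margin, SD 4 and the projected 142/71 and 119/59. The gain from closing the gap is a formal SCD claim with about 85% power to pass both tests when the drugs are equal, against 86% for SCD alone. These powers rest on the SAP's stated inputs with no loss of patients, and they exceed the SAP's 89% and 82% by about 2 to 4 points. Until that difference is explained, either the stated powers or the stated inputs are incomplete.

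**What to change.** 1. **SAP 7.1 and 7.4:** state a fixed sequence, applied at both the interim and the final analysis at the level set for that analysis. Test all ITT patients against 2 mg/g dw. Only if that passes, test SCD patients against 2 mg/g dw with the same CI, and claim non-inferiority in SCD only if both pass. Keep the non-SCD comparison descriptive. Testing all patients first keeps the declared primary test and its alpha unchanged.
2. **SAP sample-size section and 3.7:** state that the stopping trigger is the all-patient test.
3. **SAP sample-size section:** correct the 89% and 82%, or state the extra assumption behind them.

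The cost is a short addition to the SAP, with no further data and no extra alpha. It should be fixed before the interim results are seen, so that the choice of population cannot depend on them. The downside is that SCD non-inferiority cannot be claimed if the all-patient test fails. If the sponsor does not want a formal SCD claim, the SAP should say that the SCD result is supportive only.
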